## **Suicide/Homicide Procedures**

Serious neuropsychiatric symptoms have occurred in patients taking Chantix. These symptoms include changes in behavior, agitation, depressed mood, suicidal ideation, and attempted and completed suicide. While some patients may have experienced these types of symptoms and events as a result of nicotine withdrawal, some patients taking Chantix who experienced serious neuropsychiatric symptoms and events had not yet discontinued smoking. In most cases, neuropsychiatric symptoms developed during Chantix treatment, but in others, symptoms developed following withdrawal of Chantix therapy.

As a result, special caution must be taken if a participant reports an *increase in depressed mood, agitation, changes in behavior not typical for them, or **suicidal thoughts or action** since starting the study medication*. The suicide/homicide protocol will be instituted for all participants noting changes of this sort since starting Chantix.

The suicide/homicide protocol is as follows:

1. Ask participant to describe their symptoms in more detail.

*“Tell me more about what you are experiencing.”*

2. Assess the level of severity.

*“In general, would you say these symptoms are mild, moderate or severe?”*

3. Assess attribution of symptoms to the study medication.

*“Do you believe these symptoms are caused by the study medication or another cause?”*

4. Assess suicide/homicide risk

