## **Risks**

Most of the risks involved in the study relate to adverse events related to study medication. Chantix and bupropion are both approved by the Food and Drug Administration as an aid for smoking cessation. The most common adverse events associated with bupropion are headache, insomnia, rhinitis, dry mouth, and anxiety. Bupropion is associated with an increased risk (1/1000 at 300 mg/day) of seizures (GlaxoSmithKline, unpublished data). We will minimize this risk by screening out and preventing participants from using bupropion who are also currently using any additional form of bupropion, psychoactive medications, nicotine replacement therapy, fluoxetine, clonidine, buspirone, or doxepin in the past 30 days and those with: self-reported alcohol dependence within the past year; history of seizures or head trauma; history of bulimia or anorexia nervosa; pregnant (as measured by over the counter pregnancy test kit for women of child-bearing age only) or contemplating pregnancy; breast feeding; myocardial infarction in the past 30 days, and use of other forms of tobacco in the past 30 days. The most common adverse events associated with Chantix are nausea, changes in dreaming, constipation, gas, and/or vomiting. The FDA recently required new boxed warning for both these medications: people who experience any serious and unusual changes in mood or behavior or who feel like hurting themselves or someone else stop taking the medication. Chantix has no clinically meaningful drug interactions based on drug characteristics and clinical experience with the drug to date (Pfizer).

All participants requesting prescription medications, Chantix or Bupropion will be screened and medically cleared by the on-the-ground primary care physician. [name] will continue his role as reviewing study physician. [name] will provide secondary review of all screeners, and intake materials to make sure there are no contradictions to pharmacotherapy. We have a long track record of [name] reviewing all medication screeners and study documents on

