All participants in the study will be quitting smoking. Risks to all participants will be minimized through frequent monitoring through the web chat portal where participants can chat with study personnel. All participants will be given detailed instructions on how to use either the nicotine replacement therapy, Chantix or bupropion prior to distributing the cessation aids. Finally, all participants will be given a 24 hour monitored telephone number to contact in case of adverse reactions to any of the cessation aids that they are using.

Furthermore, KUMC will be in weekly contact with a clinician or nurse at the Tribal campus health center to review any adverse events or suspected adverse events. We will also be specifically asking participants about adverse events on a weekly basis (via our web –based communication system) and follow-up with phone calls to review anything reported. The following questions will be asked from participants using web-based system to report any adverse events from medications:

- “Have you had any side-effects from your pharmacotherapy this week?”
- “Have you had any urgent or emergent visits to the doctor or a hospital for health problems this week?”

- “Have you had any new unexpected health problems this week that we have not talked about?”

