## **V. Study Procedures**

### **Design Overview**

The proposed study is a randomized design in which Tribal College smokers will receive one of two internet-based interventions: 1) a culturally and individually tailored, interactive smoking cessation intervention (**I-ANBL**); or 2) internet-based healthy diet -fruit and vegetable consumption intervention (**I-FV**). Participants in both groups (I-ANBL and I-FV) will be offered pharmacotherapy (e.g. varenicline or bupropion or NRT). The primary outcome of interest will be biochemically verified continuous abstinence at 6 months. Secondary endpoints include number of quit attempts and number of cigarettes smoked (among continuing smokers), pharmacotherapy utilization, and the number of completed web-sessions. We will also examine the marginal cost-effectiveness of the intervention.

We propose the adaptation and testing of a culturally tailored smoking cessation program for tribal college students. We will finish developing the program using an iterative, CBPR process that we have used in the past to develop a successful smoking cessation program for AI.

The study will be done in three phases over a five-year period. Phase 1 will include adaptation of the program and tailored materials, including assessments of the website for scientific

accuracy, readability, cultural appropriateness, and navigability; Phase 2 will be to conduct the randomized trial and Phase 3 will consist of data analysis and dissemination.

Participants will be recruited from a Tribal college.

**Pharmacotherapy:** The PI of this study along with our AI community members agreed that all participants (I-ANBL and I-FV arms) had to be offered pharmacotherapy (varenicline or bupropion or NRT) as a component of the study design. This decision was a collaborative one between the AI tribes and the investigators who have worked with this population. The AI community will not accept placebo treatment, therefore, the interventions would not be acceptable or feasible to potential participants if a placebo was part of the study design.

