### **Plans for Assuring Compliance with Requirements Regarding the Reporting of Adverse Events (AE).**

The pharmacotherapy that will be used in this study has been approved by the Food and Drug Administration for aid in smoking cessation treatment. The adverse events associated with the TNP are few and mild and include skin irritation at the patch site and mild increases in heart rate and blood pressure. Adverse events related to nicotine gum and lozenge use are generally few and mild and can include hiccups, sore mouth and jaw, indigestion, headache, nausea, and insomnia. Studies have shown that varenicline is well tolerated, with few and mild adverse effects. The most common varenicline-related adverse effect is nausea, which is reported to be mild to moderate. Varenicline use will be monitored by the patient's primary care physician. The most common adverse effects associated with bupropion are dry mouth and insomnia. Subjects may also rarely complain of confusion, anorexia, or dizziness. Bupropion is also associated with a 1/1000 risk of seizures at the dose that will be used in this study. Factors that may increase the risk of seizures include: a history of head trauma, seizures, CNS tumors, excessive use of alcohol or cocaine, withdrawal from alcohol or benzodiazepines, and use of certain other drugs, including antipsychotics, antidepressants, theophylline, and systemic steroids. All patients will be screened for risk factors for seizures prior to recommending use of bupropion. Bupropion will only be provided to participants who have received a prescription from their primary care physician.

Participants will be prompted to discuss any adverse effects with their primary care physician or, if they do not have a primary care provider, with [name] or the on-site clinician who will work with [name]. Both subjects and physicians will be given the study office phone number (24-hour coverage) to contact study staff and/or investigators to report adverse events.

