Furthermore, KUMC will be specifically asking participants weekly about potential adverse events (via our web-based communication system). Any report of an urgent/emergent or unexpected medical encounter by a study participant would automatically trigger an inquiry by our study personnel to find out what happened, create an AE report and forward that to [name] and the on-the-ground physician to review and decide whether the AE was study or study medication related and whether participant should be taken off pharmacotherapy or should be advised to stop participating in the study.

Because the anticipated level of risk involved with all possible pharmacotherapy use is low, adverse events will be recorded and reported at the completion of the study along with other study results. In addition, serious adverse events will be monitored and handled as described below:

Definition: Consistent with the definition by the FDA, a serious adverse event includes any event experienced by a study subject while on the study medication that:

- Is fatal
- Is life-threatening (subject was at risk of death from the event as it occurred)
- Is disabling or incapacitating
- Requires inpatient hospitalization or prolongs a current hospitalization
- Is a congenital anomaly in the offspring of a subject who received the study medication
- Required intervention to prevent permanent impairment or damage

Monitoring: Information about serious adverse events experienced by study subjects will be monitored by the following means:

- Report given by study subjects to study staff either in person or by telephone
- Report given to study staff by study subjects' family or friends either in person or by telephone
- Report by the subject's physician or other health care provider involved in their care
- Report from a hospital or other healthcare facility where the study subject(s) is being treated for the serious adverse event
- Other persons that may have knowledge of such serious adverse event.

Procedure: Upon receiving report of a serious adverse event:

- The study staff will page [name] (at beeper [name]) as soon as possible
- The study staff will give the necessary information to [name]
- [name] will obtain other necessary information and complete the "MED WATCH" form for each serious adverse event
- [name] will make a decision whether to stop the study medication temporarily or permanently and inform study staff of this decision

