### Course of Action

1. If a participant reports **any** suicidal/homicidal ideation, including passive ideation (e.g., thoughts of death, would be better off dead, doesn’t care about living, etc.) or active ideation (has intent to harm, a plan, and means) advise them to stop taking the medication immediately.
2. If the participant is exhibiting active suicidal or homicidal ideation and DOES intend to harm him or herself or someone else:
  - a. Each local mental health center office provides 24 hour a day telephonic crisis response for any citizen in crisis. After discussing the person's problems on the phone the mental health professional (MHP) will decide whether a face to face evaluation is needed.
  - b. Where full time dedicated MHP teams exist, emergency crisis services are available to all persons for both telephone crisis support and face to face evaluations, where clinically indicated, on a 24/7 basis. In offices without dedicated full time crisis teams, clinicians are on call to respond to emergency requests for evaluation and dispositions only for WMMHC clients.
  - c. When a person is judged not to be in an emergency situation, as defined in Montana statute, the person may be given an emergency appointment at the local center for the next day, or referred to a local hospital for voluntary psychiatric admission, or linked with other community resources as appropriate.
  - d. If the individual has a primary therapist, who is not affiliated with the mental health center, that primary therapist will be contacted as soon as practical by the MHP.

- e. Stay with the participant until the crisis worker is able to intervene.
3. If the participant is exhibiting passive suicidal or homicidal ideation and does NOT intend to harm him or herself, the counselor should provide the participant with the **Mental Health Resource Card** and the **Crisis Referral List**. The counselor should also encourage the participant to seek support from friends, family, and possibly mental health resources.
4. If there is no suicide risk but the participant reports neuropsychiatric symptoms (increase in depression, change in mood, agitation, etc.) that are more than mild and that they attribute to the study medication, advise them to stop taking the medication immediately.

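### The suicide/homicide procedure is triggered only for Chantix users, although the protocol cites the same boxed warning for bupropion and offers bupropion in both arms

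*Protocol*

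**What the plan says.** Section VI, Suicide/Homicide Procedures, opens with a paragraph on neuropsychiatric symptoms in patients taking Chantix. It then asks for special caution when a participant reports worsening mood, agitation, uncharacteristic behaviour or suicidality "since starting the study medication". The next sentence is the operative one: "The suicide/homicide protocol will be instituted for all participants noting changes of this sort since starting Chantix". A scripted interview follows, covering symptoms, severity, attribution, ideation, plan, means, history and support.

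The Course of Action that comes after the interview does not name a drug. For symptoms without suicide risk, for example, it addresses those "that are more than mild and that they attribute to the study medication, advise them to stop taking the medication immediately".

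Section III, Risks, introduces Chantix and bupropion together and later states: "The FDA recently required new boxed warning for both these medications". It describes that warning as concerning serious changes in mood or behaviour and thoughts of harming oneself or others, with the instruction to stop the drug.

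Section V, Design Overview, offers varenicline, bupropion or NRT to participants in both arms.

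**The concern.** The protocol states a neuropsychiatric warning for two drugs and builds its response around one. A suicide-risk procedure should have an entry condition that staff can apply without interpretation. Here the entry condition leaves out users of a drug that the trial supplies and that, on the protocol's own account, carries the same warning.

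At stake is what staff do once a bupropion user reports suicidal or homicidal thoughts. If they follow the trigger as written, they do not start the structured interview, and they do not reach the steps attached to it: advice to stop the drug on any ideation, referral to crisis services, and immediate contact with the study physicians. This is a participant-safety matter and has no bearing on the statistical inference.

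**Working it through.** The point is textual, so the check is to set the statements side by side and then see whether anything else closes the gap.

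**Scope of each statement**

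| Place | Scope |
|---|---|
| Section III, Risks (boxed warning) | Chantix and bupropion |
| Section V, Design Overview (drugs offered) | Varenicline, bupropion or NRT, both arms |
| Section VI, Suicide/Homicide Procedures, opening paragraph | Chantix |
| Same section, special-caution sentence | The study medication |
| Same section, trigger sentence | Chantix |
| Section VI, Course of Action | The medication or the study medication; no drug named |

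The trigger is narrower than the boxed warning in Section III. It is also narrower than the sentence before it if *study medication* has its usual meaning in this protocol. That usual meaning is wide: Internet Session 1 in Section V speaks of any study medication, and the serious adverse event steps in Section VI use the term and name two manufacturers to be informed.

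**Does the rest of Section VI extend the trigger?** No. Its account of bupropion begins "The most common adverse effects associated with bupropion are dry mouth and insomnia" and goes on to confusion, anorexia, dizziness and seizures. It does not mention mood change or self-harm.

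**Do the general safeguards start the script?**

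- *Weekly web questions (Section III, Risks).* There are three. The first is "Have you had any side-effects from your pharmacotherapy this week"; the others ask about urgent or emergent visits and about new unexpected health problems. Number naming mood or self-harm: 0 of 3. Anything reported is followed up by telephone, so a report can reach staff.
- *Automatic inquiry (Section VI, adverse event reporting).* "Any report of an urgent/emergent or unexpected medical encounter by a study participant would automatically trigger an inquiry". Suicidal thoughts without a medical visit would not meet this condition.
- *Serious adverse events (Section VI).* Ideation without hospitalisation or another listed outcome need not qualify as serious. Other adverse events are to be reported at the end of the study.
- *Scheduled scales (Section V, Measures).* The CES-D is collected at weeks 1, 3, 5, 7 and 12 and at month 6, but the protocol states no score that prompts action.
- *24-hour telephone line and physician review (Sections III and VI).* These are open to all participants, but they do not refer to the suicide/homicide procedure.

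These routes are the same for every drug and may bring a problem to light. None starts the scripted assessment.

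**How many participants?** The protocol randomises 300 (150 per arm) and does not give the expected share choosing bupropion. Assuming 5% to 30%:

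- 0.05 × 300 = 15
- 0.30 × 300 = 90

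This counts users of the drug. Those affected are the subset who report such symptoms, and the documents give no basis for estimating that number.

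**The case against.** The strongest reply is that there is no contradiction within the section. Its opening paragraph is about Chantix alone and the next sentence follows from it, so the study medication there may simply mean Chantix. That reading is possible. It removes only the conflict within the section; the mismatch with the boxed warning in Section III remains.

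A second reply is that the Course of Action is drug-neutral on its face: it tells staff what to do when a participant reports any ideation, and it requires physician contact whatever the level of threat. A sensible member of staff might therefore apply it to a bupropion user. This has force, and it means Section VI is not without text pointing the right way. But those steps sit inside a procedure whose stated entry condition is Chantix, and staff should not have to choose between two sentences in a crisis.

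A third reply is that the restriction may be deliberate. Suicidality exclusions in Section IV apply only to Chantix, and the added Tribal clinic monitoring in Section III is also stated only for Chantix. The protocol nowhere says it is tiering the response by drug, however, and the pattern cuts both ways: a smoker excluded from Chantix for suicidal thoughts in the past 12 months meets no corresponding bar to bupropion, the drug outside the trigger.

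Two limits stand. The weekly questions are no weaker for bupropion users than for Chantix users, so the gap lies in the response and not in detection. The 5% to 30% range is an assumption, and its upper end may be generous given the long list of bupropion exclusions.

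**Conclusion.** The concern holds. As written, the trigger leaves bupropion users outside the scripted suicide/homicide assessment, although the protocol says the relevant warning covers them. This conclusion rests on the wording of Sections III, V and VI and on no assumed figure; only the range of 15 to 90 bupropion users depends on an assumption. The wording looks more like a drafting slip than a decision, though the document cannot settle that. Other safeguards reduce the practical consequence without replacing the script. The correction should be made because the possible harm is serious and the cost is close to nil.

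**What to change.** In Suicide/Homicide Procedures, change the end of the trigger sentence so that it refers to changes since starting *any study medication*. This matches the usage elsewhere in the protocol. It would also take in NRT, for which the protocol cites no such warning, but applying the script there does no harm. The minimum that follows from the protocol's own statements is *Chantix or bupropion*.

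Add one sentence to the opening rationale of that section saying that the boxed warning described under Risks also covers bupropion.

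The cost is one phrase and one sentence in an amendment, plus a note to study and clinic staff. The interview script and course of action can stay as they are, and no new form is needed. Whether bupropion should also carry suicidality exclusions is a separate clinical decision and is not part of this point.

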### **Ideation:**

*“Are you having any thoughts of harming yourself or someone else?”*

*“What are the thoughts?”*

*“How long have you been experiencing them?”*

### **Intent/Plan:**

*“Do you plan?” or “Have you thought about how you would harm yourself or someone else?”*

*“What is your plan?” or “How would you do it?”*

### **Means:**

*“Do you have the means to carry out your plan?” (e.g., access to pills, a gun, etc.)*

### **History:**

*“Have you had these thoughts before?”*

*“What have you done when you’ve felt this way?”*

*“Have you ever attempted to harm yourself or someone else?”*

*If yes, when did this occur?*

*How many times has it occurred?*

*What did you do? (e.g., take pills, gun, cut)*

*Were you hospitalized?*

### **Social Support:**

*“Who do you talk to when you’re feeling this way?”*

*“Are you currently in counseling or treatment?”*

### Course of Action

1. If a participant reports **any** suicidal/homicidal ideation, including passive ideation (e.g., thoughts of death, would be better off dead, doesn’t care about living, etc.) or active ideation (has intent to harm, a plan, and means) advise them to stop taking the medication immediately.
2. If the participant is exhibiting active suicidal or homicidal ideation and DOES intend to harm him or herself or someone else:
  - a. Each local mental health center office provides 24 hour a day telephonic crisis response for any citizen in crisis. After discussing the person's problems on the phone the mental health professional (MHP) will decide whether a face to face evaluation is needed.
  - b. Where full time dedicated MHP teams exist, emergency crisis services are available to all persons for both telephone crisis support and face to face evaluations, where clinically indicated, on a 24/7 basis. In offices without dedicated full time crisis teams, clinicians are on call to respond to emergency requests for evaluation and dispositions only for WMMHC clients.
  - c. When a person is judged not to be in an emergency situation, as defined in Montana statute, the person may be given an emergency appointment at the local center for the next day, or referred to a local hospital for voluntary psychiatric admission, or linked with other community resources as appropriate.
  - d. If the individual has a primary therapist, who is not affiliated with the mental health center, that primary therapist will be contacted as soon as practical by the MHP.

- e. Stay with the participant until the crisis worker is able to intervene.
3. If the participant is exhibiting passive suicidal or homicidal ideation and does NOT intend to harm him or herself, the counselor should provide the participant with the **Mental Health Resource Card** and the **Crisis Referral List**. The counselor should also encourage the participant to seek support from friends, family, and possibly mental health resources.
4. If there is no suicide risk but the participant reports neuropsychiatric symptoms (increase in depression, change in mood, agitation, etc.) that are more than mild and that they attribute to the study medication, advise them to stop taking the medication immediately.
5. Regardless of the level of threat, a detailed case note must be made on the Adverse Event Report Log and Drs. [name] and [name] must be contacted immediately. *Please note: **If a participant is actively suicidal, the first priority is to ensure their safety. Drs. [name] and [name] should be contacted after the Crisis Worker has intervened.***

**Plans for Assuring that any Action Resulting in Temporary or Permanent Suspension of the Research is Reported to the NCI Program Director Responsible for the Grant.** Clinical research is subject to annual review and recertification by the Human Subjects Committee of the University of Kansas Medical Center. Any action resulting in temporary or permanent suspension of the research by the Human Subjects Committee, the FDA, or other authorized governmental agencies, will be reported to the NCI program director responsible for the grant.

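### Read literally, the suicide/homicide procedure sends a participant who states intent to harm self, but lacks a plan or means, to neither the crisis step nor the referral step

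*Protocol*

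**What the plan says.** The rule is in the Protocol, Section VI, Suicide/Homicide Procedures, under Course of Action. It has five numbered steps and applies to participants who report changes in mood, behaviour or suicidal thinking since starting Chantix.

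- **Step 1** covers any suicidal or homicidal ideation and tells staff to have the participant stop the drug. It illustrates passive ideation with examples that carry no intent, and describes the other kind as "active ideation (has intent to harm, a plan, and means", three elements joined by *and*. No other description of active ideation appears in the protocol.
- **Step 2**, the crisis response, opens: "If the participant is exhibiting active suicidal or homicidal ideation and DOES intend to harm him or herself or someone else". Under it, after a telephone discussion, "the mental health professional (MHP) will decide whether a face to face evaluation is needed", and study staff are told: "Stay with the participant until the crisis worker is able to intervene".
- **Step 3**, the resource card and crisis referral list, opens: "If the participant is exhibiting passive suicidal or homicidal ideation and does NOT intend to harm him or herself".
- **Step 4** opens: "If there is no suicide risk but the participant reports neuropsychiatric symptoms".
- **Step 5** applies to everyone: "Regardless of the level of threat, a detailed case note must be made on the Adverse Event Report Log". Two physicians must also be contacted immediately. A note changes the order for one group: "If a participant is actively suicidal, the first priority is to ensure their safety", and the physicians are then called after the crisis worker has stepped in.

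**The concern.** Steps 2 and 3 should between them cover everyone with suicidal or homicidal ideation. As worded they do not. Step 2 joins two conditions (active ideation and intent), step 3 joins two others (passive ideation and no intent toward self), and the only description of *active* demands a plan and means as well as intent. A participant who says they intend to harm themselves but has no plan, or no means, falls between the two.

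The introduction to the procedure lists suicidal ideation and attempted and completed suicide among events seen with Chantix, so this is the rule staff would reach for when it matters most. Two staff members could follow the same text and act differently: one starts the crisis response and stays with the participant, while the other stops the drug and calls the physicians. The note to step 5 widens the difference, because the order of calls also depends on whether the participant counts as actively suicidal.

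A smaller point is that step 3 speaks of suicidal or homicidal ideation but tests only intent toward oneself. Step 2 and the interview questions under Ideation, Intent/Plan and History all include harm to another person.

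**Working it through.** There is no figure to reproduce. The check applies each step's stated conditions to each combination of intent, plan and means.

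**Conditions, taken literally**

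- Active = intent and plan and means (step 1).
- Step 1: any ideation.
- Step 2: active, and intent toward self or someone else.
- Step 3: passive, and no intent toward self.
- Step 4: no suicide risk, but neuropsychiatric symptoms.
- Step 5: everyone.

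**Intent to harm self**

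| Plan | Means | Step 1 | Step 2 | Step 3 | Step 4 | Step 5 |
|---|---|---|---|---|---|---|
| yes | yes | applies | applies | no | no | applies, physicians after crisis worker |
| yes | no | applies | no (not active) | no (intent present) | no (risk present) | applies |
| no | yes | applies | no (not active) | no (intent present) | no (risk present) | applies |
| no | no | applies | no (not active) | no (intent present) | no (risk present) | applies |

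So 3 of the 4 combinations reach only steps 1 and 5. If the same participants are not *actively suicidal* for the step 5 note, the physicians are called immediately and no crisis response is prescribed.

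**The same three rows with intent as the only test.** Step 2 now applies, steps 3 and 4 still do not, and step 5 applies with the physicians called after the crisis worker. The result is steps 1, 2 and 5. The two readings therefore differ by the whole of step 2 and by the order of contacts.

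**Intent toward another person only, without plan or means.** Literally this is not active, so step 2 fails. Step 3's intent condition does not exclude the participant, because it mentions only self-harm. Anyone classed as passive would receive the card and referral list despite stated intent to harm someone. With intent as the only test, step 2 catches this case, so the omission matters only if the participant is classed as passive.

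**Can the case arise from the interview?** Means has its own heading and question, so a stated plan without means is an answer staff can plainly obtain. Intent and plan share one heading and the questions there ask about a plan, so intent without a plan is harder to elicit, though a participant may volunteer it.

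**The case against.** The best reply is that the wording in step 1 is a passing gloss and not a definition. It sits in a step whose instruction is the same for active and passive ideation, and nothing says it sets the trigger for step 2. If *active* already contained intent, step 2 would not need to add intent. The capitals on DOES in step 2 and NOT in step 3 suggest that intent is the real divider, and a sensible counselor would probably act on that.

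This is a fair account of what the authors may have meant. It does not settle the text. Step 2 still joins the two conditions with *and*, and the redundancy argument cuts both ways: if active simply means intent, it is the word *active* that adds nothing.

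Other points stand and limit the finding:

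- The participant is not left unmanaged. The drug is stopped and the physicians are called, sooner than under step 2.
- Much of step 2 describes what the local mental health service offers. The direct instruction to study staff is to stay with the participant.
- In ordinary speech, someone who states intent to kill themselves is actively suicidal, and the step 5 note does not cite the three-part description.
- Exposure is narrow. Chantix is one option among several, including no drug (Section V), and Section IV bars from it anyone with a suicide attempt, suicidal thoughts or thoughts of harming others in the past 12 months.

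None of these tells staff which action comes first. The exclusion also looks back only 12 months, while the procedure concerns symptoms that emerge after starting the drug.

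**Conclusion.** The concern holds as a fault in the wording of a safety rule. Followed literally, the Course of Action gives no crisis response or referral to a participant with stated intent to harm self who lacks a plan or means. That is steps 1 and 5, against steps 1, 2 and 5 if intent alone is the test. These counts describe required actions and are not a risk estimate. The protocol gives neither Chantix uptake nor a rate of ideation, so no expected number of cases can be stated.

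The conclusion rests on reading the step 1 parenthesis as the meaning of *active* throughout. That reading is open but not forced, so confidence is moderate. The missing reference to other people in step 3 is a secondary slip. Sample size, power and type I error are unaffected. The wording should be corrected because a rule for this situation ought not to depend on which reading staff choose.

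**What to change.** 1. Trigger step 2 on any stated intent to harm self or someone else, whether or not a plan or means is present.
2. Bring the step 1 parenthesis into line, for example: *active ideation (intent to harm self or someone else, with or without a plan or means)*. The step 5 note then follows the same rule.
3. Let step 3 cover all remaining suicidal or homicidal ideation where there is no intent to harm self or someone else. The step 5 physician contact continues to apply.

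Steps 4 and 5 need no other change.

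The cost is a short protocol amendment and retraining of staff. There would be somewhat more crisis calls, some of them for participants with intent but no plan or means. Step 2a already has a mental health professional triage such calls by telephone before any face-to-face evaluation.
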